8.1.6. Pregnancy Testing

Protocol: ATI-502-AA-203

The investigator or designee will perform a urine pregnancy test for subjects who are WOCBP at the visits detailed in Schedule of Assessments (Table 3). The UPT kits provided by the Central lab have a minimum sensitivity of 25-mIU β-HCG/milliliter (mL) of urine. If the result of any post-treatment urine pregnancy test is positive, the subject will be withdrawn from the study and the subject's pregnancy documented and followed.

8.2. Adverse and Serious Adverse Events

Adverse events will be monitored throughout the study and reported on the appropriate Aclaris Therapeutics, Inc. AE eCRF.

8.2.1. Definition of Adverse Events

8.2.1.1. Adverse Event (AE)

An AE is the development of an undesirable medical condition or the deterioration of a preexisting medical condition following or during exposure to a pharmaceutical product, whether or not considered casually related to the product.

The investigator should, when certain, report a diagnosis rather than the signs, symptoms or clinically significant abnormal laboratory values associated with the AE. Otherwise, signs, symptoms or abnormal laboratory values may be used to describe the AE.

Every new episode or clinically significant worsening of a chronic condition (e.g., headaches, seasonal allergies, depression, or hypertension) should be reported as a separate AE, even if the condition is reported in the subject's medical history. Hair growth in unexpected areas, such as facial hair in women, should be reported as an adverse event.

Any CS abnormality discovered prior to the first study medication treatment (e.g. laboratory or ECG results from Visit 9 in study ATI-501-AUAT-201) should be reported as medical history, not as an AE.

All AEs that occur after any subject has been enrolled, before treatment, during treatment, or within 30 days following the cessation of treatment, whether or not they are related to the study, must be recorded in the subject's source documents and in the Aclaris' electronic case report

Date: 09NOV2018, Version 1.0 Page 48 of 80 CONFIDENTAL

Protocol: ATI-502-AA-203

form (eCRF). Changes to a subject's medical condition that occur between signing an ICF and beginning treatment should be captured in the medical history.

8.2.1.2. Serious Adverse Event (SAE)

A serious adverse event is an AE occurring during any study phase (i.e., Baseline, Treatment, Washout, or Follow-up), and at any dose of the investigational product, comparator or placebo, that fulfills one or more of the following:

- Results in death
- It is immediately life-threatening
- It requires in-patient hospitalization or prolongation of existing hospitalization
- It results in persistent or significant disability or incapacity
- Results in a congenital abnormality or birth defect
- It is an important medical event that may jeopardize the patient or may require medical intervention to prevent one of the outcomes listed above.

The term "life threatening" refers to an event in which the subject was at risk of death at the time of event; it does not refer to an event that hypothetically might have caused death if it were more severe.

Important medical events are those that may not be immediately life threatening, result in death or hospitalization, but are clearly of major clinical significance and may jeopardize the subject or require intervention to prevent one of the outcomes listed in the SAE definition above. These should also usually be considered serious.

All SAEs that occur from the time of informed consent until 30 days following the cessation of study medication dosing, whether or not they are related to the study, must be recorded on the SAE forms provided by Aclaris Therapeutics, Inc.

8.2.1.3. Unexpected adverse event

An AE is considered unexpected if it is not listed in the Investigator's Brochure or is not listed at the specificity or severity that has been observed.

8.3. Reporting Adverse Events

8.3.1. Adverse event reporting period

The investigator must start reporting non-serious AEs from the time of the subject's first dose of study medication until 30 days after the last dose of study medication. Reporting for SAEs must start when the subject signs the ICF and continue until 30 days past the subject's last dose of study medication, whether or not they are related to the study.

Any adverse events that were ongoing at the time of completion from study ATI-501-AUAT-201, will be recorded in the medical history at Visit 1.

Date: 09NOV2018, Version 1.0 Page 49 of 80 CONFIDENTAL

Protocol: ATI-502-AA-203

8.3.2. Severity

The investigator is to define the severity of each AE using the following definitions as a guideline. The investigator will consider the range of the possible severity of the event and identify the severity that is the most appropriate according to her/his medical judgment.

Mild – Awareness of signs or symptom, but easily tolerated

Moderate – Discomfort, enough to cause interference with usual activity

Severe – Incapacitating with inability to perform usual activity

8.3.3. Relationship to study medication

The investigator will determine if there is a reasonable causal relationship between the study medication and an AE or not. The investigator will use her/his best medical judgment and consider all relevant factors (e.g., temporal relationship, location of the event, the subject's relevant medical history, concomitant therapies and concurrent conditions) to determine the relationship of the AE to the study medication. The investigator will define the relationship of an AE to the study medication by selecting one of the following categories:

Related – There is a reasonable causal relationship between the study medication and the AE.

Not Related – There is not a reasonable causal relationship between the study medication and the AE.

The expression "reasonable causal relationship" is meant to convey in general that there are facts (evidence) or arguments to suggest a causal relationship (International Conference on Harmonization [ICH] E2A).

8.3.4. Procedures for reporting adverse events

At each post-enrollment visit, the investigator will question the subject to elicit AEs using a non-directive question such as "Has there been any change in your health since the previous study visit?" If appropriate, based on the subject's response to non-directed questioning to elicit AEs, the investigator will follow-up with directed questions and appropriate evaluations.

Any AE noted during the reporting period must be reported in the source documents and on the appropriate AE eCRF. AEs that are defined as "Not Related" to the study medications will be followed until they are resolved or until the subject's last study visit. AEs that are defined as "Related" to the study medications will be followed until they are resolved or, if not resolved after the subject's last study visit, until in the opinion of the investigator, the AE reaches a clinically stable outcome with or without sequelae.

8.3.5. Procedure for reporting a serious adverse event

Upon becoming aware of a SAE occurring during the SAE reporting period, whether or not related to the study medications, the investigator must:

1. Take the appropriate medical action to ensure the subject's safety.

Date: 09NOV2018, Version 1.0 Page 50 of 80 CONFIDENTAL

2. Immediately inform the Safety Monitor of the SAE by email, ensuring that the subject information is deidentified (only subject initials and subject number) to: **ProPharma**,

Email: [contact].

- 3. Print a copy of the email confirmation from ProPharma and place in the study file.
- 4. Within 24-hours complete, as fully as possible, an AE eCRF and an SAE form; e-mail the forms and any other relevant information (*e.g.*, concomitant medication eCRF, medical history eCRF, laboratory test results) to ProPharma (Aclaris Therapeutics, Inc. Safety Monitor).
- 5. Monitor and document the progress of the SAE until it resolves or, if not resolved after the subject's last study visit, until in the opinion of the investigator the SAE reaches a clinically stable outcome with or without sequelae AND the investigator and Aclaris Therapeutics, Inc. Safety and Medical Monitor agree that the SAE is satisfactorily resolved.
- 6. Inform the Aclaris Therapeutics, Inc. Safety Monitor of SAE updates, via telephone, followed by an SAE form update sent by e-mail.
- 7. Comply with the appropriate regulatory requirements and Aclaris Therapeutics, Inc. instructions regarding reporting of the SAE to the responsible Institutional Review Board (IRB) or Ethics Committee (EC).

8.4. PREGNANCY

Protocol: ATI-502-AA-203

8.4.1. Definition of Women of Child Bearing Potential (WOCBP)

WOCBP includes any female who has experienced menarche and who has not undergone successful surgical sterilization (*e.g.*, hysterectomy, bilateral tubal ligation, or bilateral oophorectomy) or is not postmenopausal. Postmenopausal is defined as ≥12 months with no menses without an alternative medical cause. WOCBP must have a negative UPT at Visit 9 (study ATI-501-AUAT-201)/Visit 1 (study ATI-502-AA-203) prior to dispensing study medication.

8.4.2. Highly Effective Methods of Birth Control

The Investigator or subinvestigator will discuss the potential risk factors associated with pregnancy and the importance of maintaining a highly effective method of contraception throughout the study with all WOCBP (for example, those which result in a low failure rate - i.e., less than 1% per year- when used consistently and correctly). All WOCBP must use a highly effective method of birth control during the study and for 30 days after the final dose of study medication in a manner such that risk of failure is minimized.

Highly effective methods include:

- Combined (estrogen and progestogen containing) hormonal contraception associated with inhibition of ovulation:
 - o oral
 - o intravaginal

Date: 09NOV2018, Version 1.0 Page 51 of 80 CONFIDENTAL

Protocol: ATI-502-AA-203

- o transdermal
- Progestogen-only hormonal contraception associated with inhibition of ovulation:
 - o oral
 - o injectable
 - o implantable
- intrauterine device (IUD)
- intrauterine hormone-releasing system (IUS)
- vasectomized partner¹
- sexual abstinence²

¹Vasectomized partner is a highly effective birth control method provided that partner is the sole sexual partner of the WOCBP trial participant and that the vasectomized partner has received medical assessment of the surgical success.

² Sexual abstinence is considered a highly effective method only if defined as refraining from heterosexual intercourse during the entire period of risk associated with the study treatments. The reliability of sexual abstinence needs to be evaluated in relation to the duration of the clinical trial and the preferred and usual lifestyle of the subject.

WOCBP must be on a highly effective method of birth control for the following timeframes prior to study entry:

- Implants (on a stable dose for \geq 30 days)
- Injectables (on a stable dose for \geq 30 days)
- Patches (on a stable dose for \geq 30 days)
- Combined oral contraceptives (on a stable dose for \geq 30 days)
- Intrauterine devices (inserted for ≥ 30 days).

Prior to trial enrollment, WOCBP must be advised of the importance of avoiding pregnancy during trial participation and of the potential risk factors associated with pregnancy while in the study. The subject must sign an informed consent form documenting this discussion. During the trial, all WOCBP will be instructed to contact the investigator immediately if they suspect they might be pregnant (*e.g.*, missed or late menstrual period).

If a subject or investigator suspects that the subject may be pregnant prior to study medication administration, the study medication must be withheld until the results of a pregnancy test are available. If pregnancy is confirmed, the subject must not receive study medication and must be discharged from the study.

If, following study medication administration, it is determined that the subject or partner of a male subject may have been or was pregnant at the time of study medication exposure (including 30 days after study medication administration) the investigator must immediately notify the Aclaris Therapeutics, Inc. Medical Monitor and record the event on a pregnancy surveillance form. While not an AE or SAE, the investigator must report every pregnancy using a pregnancy surveillance form and follow the reporting procedures described for SAE reporting.

Protocol-required procedures for trial discontinuation and follow-up must be performed on the subject unless contraindicated by pregnancy (*e.g.*, x-ray studies). Other appropriate pregnancy follow-up procedures should be considered if indicated. In addition, the investigator must report to Aclaris Therapeutics, Inc.'s Medical Monitor on the pregnancy surveillance form, follow-up

Date: 09NOV2018, Version 1.0 Page 52 of 80 CONFIDENTAL

information regarding the course of the pregnancy, including perinatal and neonatal outcome. Infants should be followed for a minimum of six weeks.

Date: 09NOV2018, Version 1.0 Page 53 of 80 CONFIDENTAL

9. STATISTICS

Protocol: ATI-502-AA-203

9.1. Sample Size and Power Calculations

The planned sample size is 80 enrolled subjects.

9.2. Analysis Populations

The Safety analysis population will be comprised of all subjects who received at least one dose of study medication. The Efficacy analysis population will include all subjects who received at least one dose of study medication using observed cases with no imputation for missing data.

9.3. Demographic and Baseline Characteristics

Subject demographic and baseline characteristics, including medical and alopecia history, prior medications and therapies and physical examination findings will be summarized using descriptive statistics.

For continuous variables, descriptive statistics (number, mean, standard deviation, standard error, median, minimum, and maximum) will be provided. For categorical variables, subject counts and percentages will be provided. Categories for missing data will be presented, if necessary.

9.4. Efficacy Analyses

Hair regrowth is determined based on both percent scalp hair regrowth (Baseline SALT – Follow-up SALT/Baseline SALT) and change in absolute percent scalp hair loss from baseline (Baseline SALT – Follow-up SALT). A responder is a subject who achieves a SALT50 or SALT75 defined as $\geq 50\%$, $\geq 75\%$ improvement in SALT score from baseline values in the ATI-501-AUAT-201 study. Durability of response will be assessed in subjects who achieved a SALT50 or SALT75 in study ATI-501-AUAT-201. Results will be summarized using descriptive statistics.

9.4.1. Primary Efficacy Analyses

For the primary endpoint, the primary efficacy variable will be the mean relative percent change from the original baseline visit in study ATI-501-AUAT-201 in the SALT score at Visit 6 (Week 24 on study ATI-502-AA-203). This represents the percentage of hair regrowth. It will be calculated as the mean of the changes from baseline SALT score to the SALT score at each visit, divided by baseline SALT score and expressed as a percentage.

9.4.2. Secondary Efficacy Analyses

The secondary efficacy endpoints will be calculated using both the current study baseline scores and the baseline scores from study ATI-501-AUAT-201. These endpoints will be evaluated at each visit and will include: the mean relative percent change from baseline in the ALODEX score (percent regrowth); the mean change from baseline in SALT and the mean change from baseline in ALODEX, the proportion of subjects achieving a \geq 50% hair regrowth compared with baseline; change from baseline in the AAA (Clinician and Subject), PhGIS, AFHA, SGIS, AIA, and treatment satisfaction questionnaires. The mean relative percent change in ALODEX

Date: 09NOV2018, Version 1.0 Page 54 of 80 CONFIDENTAL

score analysis will use the same methodology as specified for the primary efficacy analysis.

Other parameters will be summarized as detailed in the statistical analysis plan.

9.5. Safety Analyses

Protocol: ATI-502-AA-203

Safety analyses will include descriptive statistics calculated on the safety parameters using the safety population. The proportion of subjects with treatment-emergent adverse events will be tabulated and presented by Medical Dictionary for Regulatory Activities (MedDRA) System Organ Class. Vital signs and clinically significant abnormal laboratory results will also be tabulated.

Data from all enrolled subjects will be presented and summarized. Safety summaries will include listings of adverse events incidences within each MedDRA System Organ Class, and changes from pre-dose values in vital signs. Adverse event summaries will be presented showing the proportion of subjects experiencing adverse events, both overall and by MedDRA System Organ Class.

Date: 09NOV2018, Version 1.0 Page 55 of 80 CONFIDENTAL

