1.5. Study Rationale

Protocol: ATI-502-AA-203

Several published case reports have demonstrated the potential for JAK1/3 inhibitors to induce hair growth in patients with AA (Kim 2017, Craiglow 2014 and 2017, Gupta 2016, Scheinberg 2016). These AA case reports have shown promising results with oral tofacitinib and ruxolitinib treatment. However, so far, JAK inhibitors have not been shown to provide long-term efficacy after ending oral treatment. Hair shedding and substantial hair loss have been reported soon after cessation of treatment with oral JAK inhibitors (Mackay-Wiggan 2016).

Date: 09NOV2018, Version 1.0 Page 19 of 80 CONFIDENTAL

Among patients with AA, patients with higher disease burdens are unlikely to have satisfactory outcomes with current therapies. Aclaris Therapeutics, Inc. is developing ATI-502 as a treatment for stable patchy AA, AU or AT. ATI-501 is an oral prodrug that is rapidly converted presystemically to ATI-502, a potent highly selective inhibitor of Janus kinase 1 (JAK1) and Janus kinase 3 (JAK3). This study will evaluate the safety and efficacy of ATI-502 Topical Solution in the treatment of subjects with AA, AU or AT. In addition, the study will assess whether topical treatment with ATI-502 Topical Solution will maintain hair regrowth in subjects who completed 24 weeks of treatment with ATI-501 Oral Suspension or Placebo Suspension in study ATI-501-AUAT-201.

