1.6. Study ATI-501-AUAT-201

Protocol: ATI-502-AA-203

Study ATI-501-AUAT-201 is an ongoing Phase 2, multicenter, randomized study designed to evaluate the safety, tolerability and efficacy of ATI-501 for the treatment of AA, AU, or AT in adult subjects. During the screening period, subjects were assessed for eligibility into the study. Eligible subjects were male and non-pregnant, non-nursing females ≥ 18 years of age, who were in good general health and free of any known disease or physical condition which might impair evaluation of the subject. Subjects were excluded from enrollment if they had a history of or current systemic or cutaneous malignancy (except for adequately treated and well healed, and completely cleared non-melanoma skin cancers), had evidence of active or latent bacterial or viral infections (including herpes zoster or disseminated herpes zoster or disseminated herpes simplex), a history of a serious local infection within 3 months prior to baseline or were positive for active tuberculosis, HIV, Hepatitis B or C infection. Subjects with serologic evidence of Hepatitis B vaccination were allowed to participate.

Enrolled subjects were required to have a clinical diagnosis of stable AA, AU, or AT with 30% to 100% total scalp hair loss (based on SALT score at baseline) for a duration of at least 6 months up to and including 12 years. Subjects who met the entry criteria were randomized to take ATI-501 Oral Suspension, 400 mg, 600 mg, 800 mg or placebo suspension twice-daily for 24 weeks. Assessment of response to treatment is being performed at Week 4, Week 8, Week 12, Week 16, Week 20, Week 24, and post-treatment Week 28.

Subjects who complete ATI-501-AUAT-201 study visits up to and including Week 24 (Visit 9) are eligible to enter this study. At Visit 9 (in study ATI-501-AUAT-201), subjects who agree to participate in study ATI-502-AA-203, must sign consent prior to first application of topical study medication. The assessments completed at Visit 9 (study ATI-501-AUAT-201) will be entered into the source documentation for Visit 1 in study ATI-502-AA-203. Subjects who meet the ATI-502-AA-203 entry criteria will apply ATI-502 Topical Solution, 0.46% BID for 24 weeks followed by a 4-week post-treatment follow up visit.

Date: 09NOV2018, Version 1.0 Page 20 of 80 CONFIDENTAL

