ALODEX Score (after SALT) ¹¹	✓	(X) [^]		X	X	X	X	X
Vellus and Indeterminate Hair Assessment	✓	(X) [^]		X	X	X	X	X
Photography (complete scalp)	✓	(X) [^]		X	X	X	X	
Subject instructions ¹²		X	X	X	X	X		
In office study medication application		X						
Dispense study medication ¹³		X	X	X	X	X		
Collect study medication and assess compliance ¹⁴			X	X	X	X	X	
Concomitant therapies	√	(X) [^]	X	X	X	X	X	X
Adverse events	√	(X) [^]	X	X	X	X	X	X

Abbreviations: CR= Clinician Rating; ET= Early termination Visit; SR= Subject Rating

¹Visit 1 will occur on the same day as Visit 9 of study ATI-501-AUAT-201. Visit 9 procedures for study ATI-501-AUAT-201 must be completed prior to initiation of any study related activity for ATI-502-AA-203. Eligible subjects must sign consent prior to first application of topical study medication. The assessments performed for Visit 9 in study ATI-501-AUAT-201 will be entered into the source document and eCRF for Visit 1 in study ATI-502-AA-203. ATI-502-AA-203 enrollment may not be open at the time of a subject's ATI-501-AUAT-201 Visit 9. If this scenario occurs, the subject may be brought back to the clinic prior to their ATI-501-AUAT-201 Visit 10. At this visit, the subject will then be given topical treatment. Assessments marked as (X)^ represent repeat assessments that would need to be performed if the subject cannot enroll directly at Visit 9 (or within 14 calendar days of Visit 9) from study ATI-501-AUAT-201.

²A written, signed ICF must be obtained from each subject prior to performing any study related procedure.

³A physical examination includes: General appearance, examination of the head, eyes, ears, nose and throat, respiratory, cardiovascular, abdominal, extremities, musculoskeletal, lymphatic, skin (other than AA) and neurological assessment.

⁴Vital signs include oral or ear temperature, blood pressure, heart rate, respiration rate.

⁵ For WOCBP, the UPT performed at Visit 9 in study ATI-501-AUAT-201 must be negative prior to study medication application. UPT in WOCBP must also be obtained at Visits 3, 4, 5, 6, and 7 and must be negative for the subject to continue in the study.

⁶ The subject should perform assessments prior to the Investigator assessments. The investigator may assist the subject in locating a Target Patch.

⁷The subject should refer to the Baseline (Visit 2 from ATI-501-AUAT-201 and Visit 1 from ATI-502-AA-203) photographs when assessing the change over time.

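### The adverse-event table pools early topical-phase onsets with the oral drug's post-treatment period and, unlike efficacy, is not split by prior treatment

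*Combined protocol and SAP*

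**What the plan says.** - **Analysis.** Protocol section 9.5: "The proportion of subjects with treatment-emergent adverse events will be tabulated and presented by Medical Dictionary for Regulatory Activities (MedDRA) System Organ Class". Treatment-emergent is not defined there. No onset split, no summary by prior oral treatment and no tabulation by causal relationship is planned.
- **Window.** Section 8.3.1 has non-serious events reported "from the time of the subject's first dose of study medication until 30 days after the last dose of study medication". Events still ongoing when the oral study ends go to medical history, so only new onsets are at issue here.
- **Entry.** Under Table 3, footnote 1, Visit 1 is by default the same day as Visit 9 of ATI-501-AUAT-201. If enrolment is not yet open, "the subject may be brought back to the clinic prior to their ATI-501-AUAT-201 Visit 10".
- **Prior treatment.** Section 1.6: subjects were "randomized to take ATI-501 Oral Suspension, 400 mg, 600 mg, 800 mg or placebo suspension twice-daily for 24 weeks". That study's response assessments end with "Week 20, Week 24, and post-treatment Week 28".
- **Same moiety.** Section 1.5: "ATI-501 is an oral prodrug that is rapidly converted presystemically to ATI-502". Section 1.3 reports that plasma ATI-502 rose with the oral ATI-501 dose.
- **Prior-treatment split.** The Synopsis (Statistical Methods) plans pooled results plus two prior-treatment sub-groups for efficacy evaluations. I read these as prior ATI-501 and prior placebo. Nothing similar is planned for safety. The Synopsis does mention safety listings by study medication, but this study has only one.

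**The concern.** Safety of the topical solution is part of the primary objective (2.1), and the study has no concurrent control. A subject who moves from 24 weeks of oral ATI-501 to topical ATI-502 on the same day spends the first weeks on topical treatment having only just stopped the oral drug. Both products deliver ATI-502, so the nature of a systemic event does not show which exposure it followed.

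Scheduled contacts fall inside or close to that period: Visit 2 on Day 15, and Visit 3 on Day 29 (±3 days) with the first scheduled on-topical laboratory sample. Under 8.1.5, a clinically significant abnormality in that sample is an adverse event of this study. In the pooled table it would look the same as an event arising months later, or one in a subject who had only taken placebo.

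What is at stake is how the topical systemic event rate is read. The plan already treats prior treatment as relevant to efficacy but does not carry that through to safety.

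**Working it through.** The plan states no adverse-event rate, and 9.1 gives N = 80 without inputs, so there is no planned figure to reproduce. As a check on the calendar, the Table 3 treatment days equal 7 × week + 1 throughout (15, 29, 57, 113, 169, 197).

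**Inputs from the documents**
- Topical treatment: 24 weeks = 168 days (3.3).
- Reporting window: 168 + 30 = 198 days (8.3.1).
- Oral off-drug follow-up: Week 24 to Week 28 = 28 days (1.6). Visit 10 is taken to be the Week 28 visit.
- N = 80 (9.1).

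**Assumptions**
- The last oral dose is at about Visit 9.
- The oral post-treatment period is 30 days (this protocol's reporting convention applied to ATI-501) or 28 days (the oral study's follow-up).

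**Step 1: overlap in time.** Overlap = max(0, period − days from Visit 9 to first topical dose); share = overlap / 198.

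| Entry after Visit 9 | Overlap, 30-day period | Share | Overlap, 28-day period | Share |
|---|---|---|---|---|
| Same day | 30 | 15.2% | 28 | 14.1% |
| Day 14 | 16 | 8.1% | 14 | 7.1% |
| Day 27 | 3 | 1.5% | 1 | 0.5% |

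These are shares of reporting time, not of events.

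**Step 2: illustrative effect on the pooled proportion.** Let f be the share previously on ATI-501, pt the probability of a treatment-emergent event without carry-over, and pc the probability of a carry-over event. None of the three is in the documents.

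Pooled = f[1 − (1 − pt)(1 − pc)] + (1 − f)pt, so the rise = f × pc × (1 − pt).

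Equal allocation to four oral arms, and equal roll-over from them, would give 3/4 × 80 = 60 subjects, so f = 0.75.

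- Low: 0.75 × 0.05 × (1 − 0.40) = 0.0225, about 2.3 points or 1.8 of 80 subjects.
- Between: 0.75 × 0.05 × (1 − 0.20) = 0.030, that is 20.0% to 23.0%, or 2.4 subjects.
- High: 0.75 × 0.10 × (1 − 0.20) = 0.060, 6.0 points or 4.8 subjects.
- Wider inputs (f 0.5–0.9, pc 2–10%, pt 20–40%): from 0.5 × 0.02 × 0.60 = 0.006 to 0.9 × 0.10 × 0.80 = 0.072, that is 0.6–7.2 points or 0.5–5.8 subjects.

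Simply counting 5–10% of 60 (3–6 subjects, 3.8–7.5 points) would overstate the rise, because some of those subjects would have an event anyway. All these figures also assume same-day entry for every prior-ATI-501 subject.

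**Step 3: what the prior-placebo group could support.** On the same allocation it has 80 − 60 = 20 subjects. With no events, the one-sided 95% upper bound is 1 − 0.05^(1/20) = 13.9%, or 3/20 = 15% by the rule of three.

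**The case against.** The case against has real force.

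- **The 30 days are a reporting window.** Sections 8.2.1.1 and 8.3.1 say how long this study's events are collected. They do not say that events in that time are attributable to a drug, and they do not concern ATI-501. This stands: applying 30 days to the oral drug is an assumption.
- **Carry-over is not shown.** No half-life or washout is given. Section 1.3 describes pathway inhibition as more sustained during the dosing period, and 1.5 reports hair loss soon after oral JAK inhibitors are stopped. This stands: the documents do not show how long oral effects last.
- **The objective includes the sequence.** Section 2.1 asks about safety following oral treatment, and the pooled table answers that. This stands as a reason to keep the pooled table, not as a reason to omit a split.
- **Direction.** A reader might infer that the topical rate is biased upward. The documents do not support that. Entry criteria (4.1, 4.2) exclude subjects who met oral discontinuation criteria, which could lower the rate.
- **Causality assessment.** Under 8.3.3 the investigator weighs timing and history and can mark an oral-drug event as not related to study medication. This stands in part: that category also holds every other cause, and 9.5 plans no table by relationship.
- **Oral-study follow-up.** A reader might infer that a late oral signal would be lost. The oral study has its own Week 28 assessment. Its adverse-event window, and whether roll-over subjects remain under it, are not in these documents, so loss cannot be claimed.
- **Sparse cells.** Splitting 80 subjects by onset and prior arm gives small counts. This stands, and limits the table to description.

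**Conclusion.** The point holds as a gap in the safety summaries. Same-day entry, a shared active moiety and a single pooled table mean that possible oral carry-over cannot be told apart from topical events, although the plan already splits efficacy by prior treatment.

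The overlap is 14–15% of reporting time for same-day entrants who took ATI-501, less for later entrants, and does not arise for prior-placebo subjects. It depends on a 28–30 day post-oral period and a last oral dose at about Visit 9. The 2.3–6.0 point rise is an illustration on assumed inputs; neither the size nor the net direction of any bias follows from the documents.

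It might also seem to follow that systemic safety should be judged only from the later window or from prior-placebo subjects. It does not: carry-over is unproven, and about 20 subjects with no events would still leave an upper bound near 14–15%. This is a low-cost improvement to the reporting, not a defect that invalidates the safety analysis.

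**What to change.** In section 9.5:

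1. Keep the overall treatment-emergent table with every event, and state the window it uses by reference to 8.3.1.
2. Add one descriptive table of treatment-emergent events, overall and by System Organ Class, by prior ATI-501 versus prior placebo (the sub-groups already used for efficacy) and by onset 30 days or less versus more than 30 days after the last oral dose. Counting from the oral dose date handles delayed entrants correctly. Give the number of subjects at risk in each cell.
3. State that systemic events of topical ATI-502 will be read from both windows and both groups together.

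The cost is one extra table from onset dates and oral-study dosing data that the sponsor should hold. Dosing, eligibility and visits do not change. The downsides are sparse cells and that genuine early application-site reactions fall in the first window, so both windows must always be shown.
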